## **7.4 PRIMARY ENDPOINT**

The primary endpoint of this trial is the frequency of patients with drug-related AE during 52 weeks of treatment. Frequency tabulation and descriptive statistics will be used to assess the safety by summarizing drug-related AE during 52 weeks of treatment by treatment group (Empagliflozin 10 mg or 25 mg) based on TS. More details are given in [Section 7.8](#).

## **7.5 SECONDARY ENDPOINTS**

### **7.5.1 Key secondary endpoint**

This section is not applicable as no key secondary endpoint has been specified in the protocol.

### **7.5.2 Secondary endpoint**

#### Mixed model repeated measures (MMRM)

Restricted maximum likelihood-based MMRM will be performed on FAS (OC) with the following model.

HbA1c change from baseline

= overall mean + treatment + baseline HbA1c + baseline renal function + visit + treatment-by-visit interaction + baseline HbA1c-by-visit interaction + error

In the above MMRM model, “treatment”, “baseline renal function”, “visit” and “treatment-by-visit” interaction are fixed classification effects, “baseline HbA1c” and “baseline HbA1c-by-visit” interaction are covariates.

The term “baseline HbA1c” refers to the last HbA1c assessment prior to the administration of any randomised medication (HbA1c values at Visit 7) and not to the HbA1c measurement used for the stratification in the randomisation.

“Baseline renal function” is a classification variable derived from the categorization of eGFR at baseline as specified in [Section 5.4.1](#) and [Table 6.4: 1](#). For modeling purpose, eGFR categories  $<90$  and  $\geq 90$  are used in the model.

Unstructured covariance structure will be used to model the within-patient correlation due to repeated measurements. If the model fails to converge, the following covariance structure

will be tested: compound symmetry, variance components and Toeplitz. The covariance structure, with which the model converges and provides the best fit as determined by Akaike information criterion (AIC), will be used for final analysis. The Kenward-Roger approximation will be used to estimate the denominator degrees of freedom.

Because the change in HbA1c from baseline at each on-treatment visit is used as the outcome variable in the MMRM model, the above model is also used to evaluate the HbA1c change from baseline overtime.

Only the available data which are observed whilst patients are on treatment will be included in the analysis. Missing data are handled implicitly by the above statistical model, rather than by using any imputation. This approach will also additionally set to missing all values measured after the use of restricted antidiabetic medication during the trial (see Section 4.2.2 in CTP).

[REDACTED]

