7. STATISTICAL METHODS AND DETERMINATION OF SAMPLE SIZE

7.1 STATISTICAL DESIGN - MODEL

This is a 52-week, randomised, multi-centre, parallel group study to investigate the safety and efficacy of empagliflozin (10 mg or 25 mg administered orally once daily) as add-on therapy to GLP-1 RA (i.e., liraglutide) in patients with T2DM with insufficient glycaemic control.

Patients to be enrolled in this study are those with T2DM who have insufficient glycaemic control despite background monotherapy with liraglutide. Empagliflozin 10 mg or 25 mg is administrated with liraglutide over 52 weeks. Patients will be randomly assigned to empagliflozin 10 mg or 25 mg.

The primary endpoint in this trial is frequency of patients with drug-related adverse events (AE) during 52 weeks of treatment. The secondary endpoint in this study is the change from baseline in HbA1c after 52 weeks of treatment.

Based upon these design considerations, the trial will be analysed using descriptive statistics for the primary endpoint. For the secondary endpoint, the HbA1c changes from baseline is considered as normally distributed based on experiences with similar endpoints in other trials and literature data. Therefore, the statistical model used for the secondary endpoint is a restricted maximum likelihood (REML)-based mixed model with repeated measures (MMRM) including the fixed effects treatment, baseline renal function, prior use of antidiabetic agents, visit, treatment-by-visit interaction and the covariate baseline HbA1c, baseline HbA1c-by-visit interaction.

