7.3.2 Secondary endpoint analyses

HbA1c

The change from baseline in HbA1c after 52 weeks of treatment will be calculated on FAS by treatment using MMRM. The statistical model is as follows:

HbA1c change from baseline = overall mean + treatment + baseline HbA1c + baseline renal function + prior use of antidiabetic agents + visit + treatment-by-visit + baseline HbA1c-by-visit + error

Analyses will include "treatment", "baseline renal function", "prior use of antidiabetic agents", "visit" and "treatment-by-visit" interaction as fixed effects, "baseline HbA1c", and "baseline HbA1c-by-visit" interaction as covariates. The term "baseline HbA1c" refers to the last HbA1c assessment prior to the administration of any randomised medication (HbA1c values at Visit 7) and not to the HbA1c measurement used for the stratification in the randomisation. "Baseline renal function" will be a classification effect derived from the categorisation of eGFR at baseline. Regarding "prior use of antidiabetic agents", patients will be classified as liraglutide only, OAD only or liraglutide plus OAD. An unstructured covariance structure will be used to model the within-patient measurements. If the analysis fails to converge, the following covariance structure will be tested: compound symmetry, variance components and Toeplitz. The covariance structure converging to the best fit, as determined by Akaike's information criterion, will be used. The Kenward-Roger approximation will be used to estimate the denominator degrees of freedom. This model will also be used to evaluate the change from baseline in HbA1c overtime during the 52-week treatment period.

Only the available data which were observed whilst patients were on treatment will be included in the analysis. Missing data are handled implicitly by the above statistical model, rather than by using any imputation. This approach will also additionally set to missing all values measured after the restricted antidiabetic medication during the trial (See Section 4.2.2)

The last available on-treatment HbA1c value is defined as the last available HbA1c value measured up to a period of seven days after the last dose of the randomised study medication or the last available HbA1c value prior to the restricted antidiabetic medication during the trial (See Section 4.2.2).

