7.6 RANDOMISATION

The trial will be performed as a double-blind design with respect to the two active dose groups of empagliflozin. Eligible patients assessed by investigator will be randomised in blocks to the two study treatments in a 1:1 ratio. The randomisation will be stratified by the following factors:

- Pre-randomisation HbA1c value (<8.0%, ≥8.0%) using the Visit 1 HbA1c values for patients pre-treated with liraglutide alone and Visit 6 HbA1c values for other patients
- Pre-randomisation eGFR value (≥90 mL/min/1.73m², 60 to <90 mL/min/1.73m², 45 to <60 mL/min/1.73m²) calculated based on Visit 6 creatinine values.

The randomisation of patients to the treatment groups will be performed via an IRT. BI will arrange for the randomisation as well as packaging and labelling of trial medication. The randomisation list will be generated using a validated system, which involves a pseudorandom number generator and a supplied seed number so that the resulting allocation of medication numbers to treatment is both reproducible and non-predictable. The access to the randomisation codes will be controlled and documented.

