7.7 DETERMINATION OF SAMPLE SIZE

The draft version of Japanese guideline 'Clinical Evaluation Guidelines for Antihyperglycemic Drugs' [R15-2907] requires one year long-term study on background therapies with several approved antidiabetic drugs. The guideline requires observing 50 to 100 patients during one year for each background therapy. The sample size for this trial was determined according to the outcome of the PMDA consultation on December 2014. At least 50 patients as 52-week completers including two doses were necessary for the background therapy with GLP-1 RA for safety evaluation.

Based on the above, and allowing for a discontinuation/dropout rate of approximately 20% during the trial, the sample size for empagliflozin 10 mg and 25 mg were determined at 32 per arm in the GLP-1 RA background group.

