### **3. INTRODUCTION**

As per ICH E9, the purpose of this document is to provide a more technical and detailed elaboration of the principal features of the analysis described in the protocol, and to include detailed procedures for executing the statistical analysis of the primary and secondary variables and other data.

This TSAP assumes familiarity with the Clinical Trial Protocol (CTP), including Protocol Amendments. In particular, the TSAP is based on the planned analysis specification as written in CTP Section 7 “Statistical Methods and Determination of Sample Size”. Therefore, TSAP readers may consult the CTP for more background information on the study, e.g., on study objectives, study design and population, treatments, definition of measurements and variables, planning of sample size, randomization.”

SAS® Version 9.4 will be used for all analyses.

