**4. CHANGES IN THE PLANNED ANALYSIS OF THE STUDY**

No changes in the planned analysis.

[figure not shown]

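### The SAP drops prior antidiabetic use from the HbA1c model that the protocol specifies, while stating that nothing in the planned analysis has changed

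*SAP*

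**What the plan says.** Protocol 7.1 describes a REML-based mixed model for repeated measures with "fixed effects treatment, baseline renal function, prior use of antidiabetic agents, visit, treatment-by-visit interaction" plus baseline HbA1c and its interaction with visit. Protocol 7.3.2 writes the model out, including "baseline renal function + prior use of antidiabetic agents + visit + treatment-by-visit + baseline HbA1c-by-visit + error", and defines the levels of the prior-use factor: "patients will be classified as liraglutide only, OAD only or liraglutide plus OAD". The synopsis also carries the factor.

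SAP 7.5.2 gives the model as "overall mean + treatment + baseline HbA1c + baseline renal function + visit + treatment-by-visit interaction + baseline HbA1c-by-visit interaction + error". The sentence after it, which lists the classification effects and covariates, leaves prior use out as well.

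SAP Section 3 states that "the TSAP is based on the planned analysis specification as written in CTP Section 7". The whole of SAP Section 4 is "No changes in the planned analysis".

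**The concern.** The two governing documents define the adjusted HbA1c change differently, and the SAP's own statement on changes is wrong as printed. If both models stay available, choosing between them after unblinding would be a choice made with the data in view.

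The factor has a reason to be in the model. It corresponds to inclusion criteria 2-A, 2-B and 2-C, which are three routes to baseline: liraglutide alone straight into the placebo run-in, liraglutide plus one OAD through a 10-week washout, and one OAD through a 14-week switch to liraglutide. It is also not balanced by design. In protocol 7.6, "The randomisation will be stratified by the following factors" is followed only by pre-randomisation HbA1c and eGFR. With 32 patients per arm, balance on entry route is left to chance.

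**Working it through.** **1. Term-by-term comparison**

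| Term | Protocol 7.3.2 | SAP 7.5.2 |
|---|---|---|
| Treatment | yes | yes |
| Baseline HbA1c | yes | yes |
| Baseline renal function | yes | yes (two eGFR groups, split at 90) |
| Prior use of antidiabetic agents (3 levels, 2 df) | yes | **no** |
| Visit | yes | yes |
| Treatment-by-visit | yes | yes |
| Baseline HbA1c-by-visit | yes | yes |

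Prior use is the only term by which the two models differ. The SAP equation and list of effects are printed in full, with the redacted block after the HbA1c model text, so redaction does not explain the gap. The protocol's amendment log does not remove the factor.

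**2. Sample size**

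Protocol 7.7 needs 50 completers over both doses, "allowing for a discontinuation/dropout rate of approximately 20% during the trial". This reproduces: 25 / (1 - 0.20) = 31.25, rounded up to 32 per arm. Expected completers per arm are 32 × 0.8 = 25.6, about 26. The model question does not affect this figure.

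**3. Effect on the dose difference at Week 52**

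Assumptions, none of them in the documents: residual SD σ = 0.7% HbA1c, and a gap g between the extreme prior-use groups in 52-week change that remains after adjustment for Visit 7 HbA1c, with the middle group halfway. The check simulates a Week 52 analysis of covariance (treatment, baseline HbA1c, two-level renal function), with and without the factor.

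The results can be followed by hand. With equal groups the factor has variance g²/6. If it is left out, that variance joins the residual:

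SE without ≈ 1.011 × √(σ² + g²/6) × √(2/n)

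Here 1.011 = 0.177/0.175 is the small loss to the other covariates, and 0.175 = 0.7 × √(2/32). For g = 0.6: 1.011 × √(0.49 + 0.06) × 0.25 = 0.187.

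The variance of the difference between the two models' estimates is about (g²/6)(2/n) + (0.180² - 0.177²). For g = 0.6: 0.00375 + 0.0011 = 0.00485, so the SD is 0.070. The value exceeded in one trial in ten is 1.645 × 0.070 = 0.11.

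| n per arm | Shares | g | SE without | SE with | Without vs with | Estimates differ by at least, 1 in 10 |
|---|---|---|---|---|---|---|
| 32 | equal | 0 | 0.177 | 0.180 | -2% | 0.05 |
| 32 | equal | 0.3 | 0.180 | 0.180 | 0 | 0.08 |
| 32 | equal | 0.6 | 0.187 | 0.180 | +4% | 0.11 |
| 32 | equal | 0.9 | 0.200 | 0.180 | +11% | 0.16 |
| 26 | equal | 0.6 | 0.209 | 0.201 | +4% | 0.13 |
| 32 | 60/25/15% | 0.6 | 0.186 | 0.180 | +3% | 0.11 |

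The one-in-ten column shows the tail. Median differences at 32 per arm with equal shares are about 0.015, 0.02, 0.04 and 0.06 to 0.07 at the four gaps.

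**4. Per-arm adjusted means, 32 per arm**

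With no gap, the SE is 0.124 without the factor and 0.125 with it, if means are weighted by the observed margins. With 60/25/15% shares and equal weights it is 0.139 (0.139/0.124 = 1.12). At g = 0.6, equal weighting also moves the mean: (0 + 0.3 + 0.6)/3 = 0.30, against 0.25 × 0.3 + 0.15 × 0.6 = 0.165, a shift of about 0.14.

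**The case against.** The strongest reply is that little depends on this.

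- **Low consequence.** Protocol 7.2 rules out confirmatory testing, the endpoint is secondary, and under randomisation both models estimate the dose difference without bias. The SAP is the later and more detailed document and states one unambiguous model, so the practical defect may be one missing line in Section 4. This stands as a limit on severity.
- **The gaps are assumed.** All routes require at least 10 weeks of liraglutide 0.9 mg/day before run-in, so the residual gap may be small. At gaps of 0 to 0.3, omission costs no precision. A gap of 0.9 would exceed the largest placebo-subtracted HbA1c reduction cited in protocol 1.2 (0.72%). This also stands.
- **Restoring the term is not always better.** The protocol enters prior use without a visit interaction. If the gap fades (0.6, 0.3, 0.1 and 0 over the four HbA1c visits, with an assumed between-visit correlation of 0.7), the Week 52 SE is about 0.182 to 0.183 with the factor and 0.177 to 0.178 without. This bears on which model to choose, not on whether the documents agree.
- **The reduction may be deliberate.** The SAP also groups eGFR into two classes for modelling, and its lipid models omit prior use too. That suggests a choice, but a deliberate change still belongs in Section 4.
- **Redacted text may hold related analyses.** A sensitivity analysis by prior use cannot be called absent. It would not remove the conflict between SAP 7.5.2, SAP Section 4 and protocol 7.3.2.

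**Conclusion.** The concern holds. The protocol and SAP give different models for the only secondary endpoint, and the SAP says there is no difference. That conclusion comes from the text and needs no assumption.

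The numerical effect is small if the entry routes hardly differ and moderate if they do. It rests on the assumed SD of 0.7 and the assumed gaps, and the middle of the range is more plausible than the 0.9 end. No error rate is affected, and neither is the sample size or the primary safety analysis. This should be fixed before unblinding, but it does not threaten the trial.

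**What to change.** Restore prior use of antidiabetic agents, with its three levels, as a fixed classification effect in SAP 7.5.2, in both the equation and the list of effects. If the reduced model is intended, record the change and its reason in SAP Section 4 before unblinding, and run the protocol 7.3.2 model as a sensitivity analysis. The same Section 4 entry should cover the two-class eGFR grouping, since protocol 7.3.2 refers only to the categorisation of eGFR.

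The cost is two SAP lines, two model degrees of freedom and no new data. If the factor is not prognostic, the SE of the dose difference rises by about 2% (0.177 to 0.180). As an optional safeguard, state that per-arm adjusted means are weighted by the observed margins. This avoids the roughly 12% rise in per-arm SE (0.124 to 0.139) that equal weighting would bring with unequal groups. The main correction does not depend on it.

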## **7.8 SAFETY ANALYSIS**

All safety analyses will be performed on the TS.

### **7.8.1 Adverse events**

AEs will be coded using the most recent version of the Medical dictionary for regulatory Activities (MedDRA) coding dictionary.

The analyses of AEs will be descriptive in nature. All analyses of AEs will be based on the number of patients with AEs and not on the number of AEs. For this purpose, AE data will be combined in a 2-step procedure into AE records.

In a first step, multiple AE occurrence data on the eCRF will be collapsed into AE episodes provided that all of the following applies:

- The same MedDRA lowest level terms are reported for the occurrences
- The occurrences are time-overlapping or time-adjacent (time-adjacency of 2 occurrences is given if the second occurrence started on the same day or on the day after the end of the first occurrence. Hypoglycaemic events are only collapsed if they occur within 12 hours of each other. The 12 hour period will begin with the first hypoglycaemia onset time. If another event occurs outside this initial 12 hour window a new period for the collapsing will begin.)
- Treatment is not changed between the onset of the occurrences or treatment is changed between the onset of the occurrences, but no deterioration is observed for the later occurrence

In a second step, AE episodes will be condensed into AE records provided that the episodes have been reported with the same term on the respective MedDRA level and that the episodes are assigned to the same treatment. For further details on summarisation of AE data, please refer to the guideline “Handling and summarisation of AE data for CTRs and integrated summaries” [\(2\)](#).

#### 7.8.1.1 Assignment of AEs to treatment

The analysis of AEs will be based on the concept of treatment emergent AEs. That means that all AEs occurring between first drug intake till last drug intake + residual effect period (7 days for this trial) will be assigned to the randomised treatment. All AEs occurring before first drug intake will be assigned to ‘screening’ and all AEs occurring after the residual effect period will be assigned to ‘post-treatment’.

#### 7.8.1.2 Analysis of other significant AEs

Other significant AEs will be reported and summarised according to ICH E3 [\(3\)](#). AEs classified as “other significant” will include those non-serious AEs with:

- “action taken = discontinuation” or “action taken = reduced”, or
- Marked haematological and other lab abnormalities or lead to significant CT as identified by the Clinical Monitor/Investigator at a medical quality review meeting or BRPM.

#### 7.8.1.3 AE summaries

An overall summary of AEs will be presented.

The frequency of patients with AEs will be summarised by treatment, primary SOC and PT. AEs will also be reported by intensity. Separate tables will be provided for patients with drug-related AEs, for patients with AEs leading to discontinuation, for patients with serious AEs, for patients with other significant AEs and for patients with AESI.

The SOCs will be sorted according to the standard sort order specified by European medicines agency, PTs will be sorted by frequency (within SOC).

#### 7.8.1.4 Analysis of hypoglycaemic events

The investigator will record for each AE whether it represents a hypoglycaemic event and, if so, record additional information to assess the intensity of the hypoglycaemic event as described in CTP, Section 5.3.3. On the basis of this information the hypoglycaemic event will be classified as:

- asymptomatic hypoglycaemia: event not accompanied by typical symptoms of hypoglycaemia but with a measured plasma glucose concentration  $\leq 3.9$  mmol/L (70 mg/dL),
- documented symptomatic hypoglycaemia with a measured plasma glucose concentration  $\geq 3.0$  mmol/L and  $\leq 3.9$  mmol/L ( $\geq 54$  mg/dL and  $\leq 70$  mg/dL): event accompanied by typical symptoms of hypoglycaemia,
- documented symptomatic hypoglycaemia with a measured plasma glucose concentration  $< 3.0$  mmol/L ( $< 54$  mg/dL): event accompanied by typical symptoms of hypoglycaemia but no need for external assistance,
- severe hypoglycaemic episode: event requiring the assistance of another person to actively administer carbohydrate, glucagon or other resuscitative actions.
- symptomatic hypoglycaemia and plasma glucose concentration  $> 3.9$  mmol/L (70 mg/dL)
- symptomatic hypoglycaemia and plasma glucose concentration not measured

The frequency of patients with hypoglycaemia according to investigator's judgement will be summarised by primary SOC and PT.

Confirmed hypoglycaemic AE is defined as hypoglycaemic AE with glucose value available and below 70 mg/dL or where assistance is required.

Summaries of confirmed hypoglycaemic AEs will include total number of hypoglycaemic AEs (asymptomatic and symptomatic), severity and intensity of the worst episode, action taken, minimum glucose level of worst episode, time to onset of first episode, and number of episodes per patient (asymptomatic and symptomatic).

Subgroup analyses of hypoglycaemic AEs with respect to age category, rescue therapy and renal function will be performed.

Summary table will include rate of confirmed hypoglycaemic AEs by severity, by age categories, and by renal function. For subgroup of age categories and renal function, time at risk for each group will be used.

Time to the onset of the first hypoglycaemia will be analysed by Kaplan-Meier estimates. The Kaplan-Meier analysis will be performed based on confirmed AEs.

Different summaries will be shown for the number of patients with hypoglycaemia (symptomatic, asymptomatic reported as AE, or asymptomatic reported as non-AE), severity of the worst episode, minimum glucose level of worst episode, time to onset of first episode, and number of episodes per patient in the CTR, Appendix 16.1.9.2.

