Proprietary confidential information © 2017 Boehringer Ingelheim International GmbH or one or more of its affiliated companies

Safety laboratory parameters – whole blood, serum or plasma

(continued)

Bone Marker (only at selected visits)

iPTH

Table 5.3.3: 1

- 25OH Vitamin D
- NTx in Urine

FFA and Ketone bodies (only at selected visits)

- Total ketone body
- Acetoacetic acid
- 3-hydroxybutyric acid
- Free fatty acid (FFA)

Table 5.3.3: 2 Safety laboratory parameters – urine

Urinalysis

Semi quantitative (dipstick)

- Nitrite*
- Protein
- Ketone
- Urine pH
- Leukocyte esterase (for WBC)*

Quantitative

- Albumin
- Creatinine

Microscopic analysis

Will be performed as reflex test if any of the semi quantitative tests/dispsticks are abnormal:

- Urine RBC/Erythrocyte
- Urine WBC/Leukocytes
- Urine sediment microscopic examination
- Urine culture (including antibiogram test):
 - reflex test triggered by positive leukocyte esterase (for WBC) and/or nitrite in the semi-quantitative test/dipstick

Albumin/creatinine ratio in spot urine will be calculated at the central lab.

Glomerular filtration rate

The eGFR will be derived from serum creatinine values for Japanese equation: eGFR (mL/min/1.73m²) = 194 x [Screatinine (mg/dL)]^{-1.094} x [age]^{-0.287} x [0.739 if patient is female]

Renal function impairment will be classified in the following way:

- No renal function impairment: eGFR >90 mL/min/1.73m²;
- Mild renal function impairment: eGFR 60 to <90 mL/min/1.73m²;
- Moderate renal function impairment: eGFR 30 to <60 mL/min/1.73m²;
- Severe renal function impairment: eGFR <30 mL/min/1.73m².

^{*} Nitrite and leukocyte esterase (for WBC) will be determined both locally on site (not recorded in eCRF) and via central lab. A positive result at site triggers the sampling of mid-stream urine for urine culture.

These classes of renal impairment will be the basis for stratification of subgroup analysis.

Pregnancy testing

Pregnancy testing (urine) will be performed in female patients of child bearing potential only according to the time points indicated in the flow chart.

Criteria for hypoglycaemic events

Every episode of glucose concentrations ≤70 mg/dL (3.9 mmol/L) should be documented in the eCRF with the respective time and date of occurrence. Any hypoglycaemia with glucose concentrations <54 mg/dL (<3.0 mmol/L) and all symptomatic and severe hypoglycaemias should be documented as an AE "hypoglycaemic event".

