For the analysis, all hypoglycaemias will be classified according to the following criteria:

- Asymptomatic hypoglycaemia: event not accompanied by typical symptoms of hypoglycaemia but with a measured glucose concentrations ≤70 mg/dL (3.9 mmol/L)
- Documented symptomatic hypoglycaemia with glucose concentrations ≥54 mg/dL and ≤70 mg/dL (≥3.0 mmol/L and ≤3.9 mmol/L): event accompanied by typical symptoms of hypoglycaemia
- Documented symptomatic hypoglycaemia with glucose concentrations <54 mg/dL (<3.0 mmol/L): event accompanied by typical symptoms of hypoglycaemia but no need for external assistance
- Severe hypoglycaemic episode: event requiring the assistance of another person to actively administer carbohydrate, glucagon or other resuscitative actions

Follow-up on suspicion for urinary tract infections

Patients having a history of chronic/recurrent urinary tract infections (UTIs) or genital tract infections (GTIs) or an acute episode of UTI or GTI at screening will be identified and this condition has to be documented as medical history or baseline condition in the eCRF, respectively.

For documentation of acute urinary tract infections during trial conduct, the following measures have to be taken:

- In any case of suspected UTI (symptomatic or asymptomatic) a urine culture sample has to be taken and sent to the central lab for confirmation of the diagnosis (including antibiogram).
- To be able to identify asymptomatic UTIs immediately, a dipstick-test (leukocyte esterase [for WBC] and Nitrite) will be performed at the site at each safety visit with urinalysis. In case of a positive result at site, a urine culture sample has to be taken and sent to the central lab for confirmation of the diagnosis (including antibiogram).

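### SAP 7.8.1.4: the hypoglycaemia classes include 70 mg/dL but the confirmed definition excludes it, so an unassisted event at exactly 70 drops out of the confirmed-only outputs

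*SAP*

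**What the plan says.** Protocol 5.3.3 sets the recording rule: "Every episode of glucose concentrations ≤70 mg/dL (3.9 mmol/L) should be documented in the eCRF". It also sets the rule for which episodes become adverse events: "Any hypoglycaemia with glucose concentrations <54 mg/dL (<3.0 mmol/L) and all symptomatic and severe hypoglycaemias should be documented as an AE". For analysis, its asymptomatic class runs up to and including 70 mg/dL, and the upper symptomatic class is "Documented symptomatic hypoglycaemia with glucose concentrations ≥54 mg/dL and ≤70 mg/dL".

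SAP 7.8.1.4 repeats these classes with the same inclusive limit. It adds two residual classes: symptomatic events with glucose above 70 mg/dL, and "symptomatic hypoglycaemia and plasma glucose concentration not measured". It then introduces a term that the protocol's hypoglycaemia criteria and safety-analysis section do not define: "Confirmed hypoglycaemic AE is defined as hypoglycaemic AE with glucose value available and below 70 mg/dL or where assistance is required".

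That term governs the summaries of confirmed events and two further outputs:

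- Rates: "Summary table will include rate of confirmed hypoglycaemic AEs by severity, by age categories, and by renal function".
- Time to first event: "The Kaplan-Meier analysis will be performed based on confirmed AEs".

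Other outputs are not stated to be limited to confirmed events. They are the investigator-judged table by system organ class and preferred term, the summaries for CTR Appendix 16.1.9.2, and the subgroup work: "Subgroup analyses of hypoglycaemic AEs with respect to age category, rescue therapy and renal function will be performed".

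**The concern.** The classes that define a documented low glucose include 70 mg/dL, and the confirmed rule excludes it. An event can therefore be a documented symptomatic hypoglycaemia under one paragraph of SAP 7.8.1.4 and unconfirmed under another, although its glucose was measured and lies within the class limit.

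At stake is the consistency of the hypoglycaemia reporting in a trial whose primary purpose is safety. The appendix summaries cover several of the same measures as the confirmed summaries (severity and minimum glucose of the worst episode, time to first episode, episodes per patient). A reader comparing the two could find a difference at 70 mg/dL that the SAP does not explain.

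**Working it through.** The plan gives no figure to reproduce here, so the check applies the SAP rules as written to values around the limit.

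**Inputs**

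- Classes (Protocol 5.3.3, SAP 7.8.1.4): asymptomatic, ≤70 mg/dL; symptomatic, <54; symptomatic, ≥54 and ≤70; symptomatic, >70; symptomatic, not measured; severe, if assistance is needed.
- Confirmed, as written: glucose available and <70 mg/dL, or assistance required.
- Confirmed, aligned: glucose available and ≤70 mg/dL, or assistance required.

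**Grid.** Six glucose states (53, 54, 69, 70, 71 mg/dL, not measured) × symptoms yes/no × assistance yes/no = 6 × 2 × 2 = 24 cells. The 12 cells with assistance are severe, and are confirmed under either rule. The 12 cells without assistance are:

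| Glucose (mg/dL) | Symptoms | Class | Confirmed, <70 | Confirmed, ≤70 |
|---|---|---|---|---|
| 53 | no | asymptomatic | yes | yes |
| 53 | yes | symptomatic <54 | yes | yes |
| 54 | no | asymptomatic | yes | yes |
| 54 | yes | symptomatic 54–70 | yes | yes |
| 69 | no | asymptomatic | yes | yes |
| 69 | yes | symptomatic 54–70 | yes | yes |
| **70** | no | asymptomatic | **no** | **yes** |
| **70** | yes | symptomatic 54–70 | **no** | **yes** |
| 71 | no | none | no | no |
| 71 | yes | symptomatic >70 | no | no |
| not measured | no | none | no | no |
| not measured | yes | symptomatic, not measured | no | no |

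Two of the 24 cells differ, both at exactly 70 mg/dL without assistance.

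**Which of the two arises in practice.** Protocol 5.3.3 requires every symptomatic episode to be recorded as an AE, so the symptomatic cell is a reportable event. An asymptomatic episode at 54 to 70 mg/dL need not be an AE, so that cell matters only if the investigator reports it as one.

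**Units.** The classes state 70 mg/dL directly, so membership does not depend on conversion. As a side check, the documents' pairs 54/3.0 and 270/15.0 each give 18.0 mg/dL per mmol/L. Then 70 / 18.0 = 3.89 mmol/L, which is within ≤3.9, and 3.9 × 18.0 = 70.2 mg/dL, which is not below 70.

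**Direction.** Every event confirmed under <70 is also confirmed under ≤70. The strict rule can therefore only reduce confirmed counts and rates or leave them unchanged, and can only postpone the first confirmed event or leave it unchanged.

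**The case against.** Confirmed is a separate term with its own rule, and nothing requires it to equal the union of the ≤70 classes. Assistance alone confirms an event, and unassisted events above 70 or without a measurement are never confirmed, so the definition does not mirror the classes in any case. This stands: it is a mismatch of limits and not a logical contradiction.

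The effect may also be nil. The trial randomises 64 patients, Protocol 2.3 rates the risk of hypoglycaemia as low, and an affected event must be a reported AE, unassisted, at exactly 70 mg/dL. It would still appear in the general AE tables and the investigator-judged table, and could appear in the subgroup analyses and appendix summaries. This stands too, and it limits the importance of the point.

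The strict limit might come from a company standard or the analysis data set plan, neither of which is available, or be loose wording that is programmed as ≤70. That cannot be excluded. It does not repair the text, because a programmer following the SAP literally would code <70, and nothing visible shows that the difference is deliberate.

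Finally, the unit pairs are rounded: the 250/14 pair in Protocol 2.3 gives 17.86, and 70 / 17.86 = 3.92 mmol/L. That pair is coarsely rounded, and the point rests on the stated mg/dL limits, not on the conversion.

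**Conclusion.** The concern holds as a minor inconsistency. Followed literally, SAP 7.8.1.4 classifies an unassisted AE at exactly 70 mg/dL as hypoglycaemia and omits it from the confirmed-only outputs.

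Its numerical size cannot be computed from the documents and may be zero. If glucose is recorded in whole mg/dL, which is an assumption, 70 is the only value affected. Confidence is high about the wording; whether any event will actually be lost depends on the data and on how the rule is programmed.

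The primary endpoint, the HbA1c analysis and the sample size do not use the definition, and Protocol 7.2 plans no confirmatory testing.

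**What to change.** Before database lock, define a confirmed hypoglycaemic AE in SAP 7.8.1.4 as one with an available glucose value ≤70 mg/dL (≤3.9 mmol/L) or requiring assistance, and set the program condition to match. If the stricter limit is intended, state that and its reason, and footnote the confirmed summaries, the rate table and the Kaplan-Meier output to say that unassisted events at exactly 70 mg/dL are excluded.

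The cost is one symbol in the SAP and one line of program, with no change to trial conduct or data collection. The confirmed count may rise slightly. Aligning the limits will not make all class totals equal the confirmed totals, because unassisted events above 70 mg/dL or without a measurement remain classified but unconfirmed; a short note to that effect would help the reader.
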